**E. 5. Data Safety and Monitoring Plan (DSMP)**

The VA's Centralized Data Monitoring Committee (DMC) will monitor this study. The DMC focuses on participant safety and accrual as well as on statistical issues. In general, the DMC will serve as an oversight committee, reviewing any modifications to the research design and conduct of the study and making recommendations.

Regarding the safety of participants, the DMC will review new risk management protocols and modifications to risk management protocols. The DMC will also review procedures and decisions regarding the adequate protection of specific participants when investigators move into risk management protocols because of adverse events or clinical deterioration. When appropriate, the DMC will serve as final arbiters of whether individual participants should be removed from the protocol.

The DMC will be in contact at least once per year with the PI and Co-I's in order to review progress reports and discuss issues relevant to study safety. Following each meeting, a summary of the board's review will be provided to the research team. They will also be available to review emerging data (in the study or the literature) which may alter the risk/benefit ratio and will be empowered to decide upon continuation, discontinuation, or termination of the study. In addition, study enrollment data will be submitted to the DMC on a quarterly basis in order for the DMC to monitor recruitment success on the project.

Data Monitoring Plan. Data will be collected using standardized forms and will only be identified using the participants ID number (no names or identifying information will be on the forms). The codes that link the names of participants and their ID numbers will be kept confidential by the site PI's in a secured, locked cabinet located within their office. These data will only be accessible to the site PI's and staff directly working with the study. All data will be entered on-line, with 100% review by the project coordinator in those instances where a

discrepancy occurs during double entry. Data will be double-entered by trained staff member, and data entry discrepancies will be corrected by the Project Coordinator, based on source documents. The quality of the data will be monitored on an ongoing basis.

Data quality will be monitored by inspection of the completed forms by a research assistant and any problems detected will be discussed with the PI. Interviewer reliability will be assessed using digital recordings of diagnostic assessments. Adherence to the intervention will be monitored using digital recordings of sessions and weekly supervision. If diagnostic and/or intervention drift is observed, staff will be retrained until acceptable reliability is reached.

**Safety Monitoring Plan.** During the first in-person screening, potential participants will undergo a comprehensive screening to determine their eligibility for, and safety for, their participation in the study, following the provision of informed consent. Attention will be placed on current suicidal risk. Individuals who are judged to be at risk for suicide will be excluded from participation in the study and will be provided with appropriate clinical referrals. Should suicidal risk increase during treatment, the therapists will consult with the PIs to determine whether the increased suicidal ideation can be managed within the clinical protocol or whether other steps will need to be taken to protect the participant.

If a participant is assessed to be at risk for suicide, treatment staff will immediately locate the site PI, who are both licensed psychologist and maintain clinical credentials at their respective medical centers, and will be on-site when assessment sessions are conducted. At that point, the site PI will intervene by a) following up with direct questions about suicidal behaviors, b) assess mental status by asking about psychotic symptoms, mood symptoms and drug and alcohol use, c) schedule extra contacts if necessary, emphasizing problem solving, d) help the participant generate short-term objectives, and e) negotiate an action plan. The action plan will be collaboratively generated by [name] and the participant. The plan will address what actions need to be taken in the succeeding days to solve the problems that precipitated suicidal behavior. The plan will also address the use of voluntary or involuntary hospitalization, if necessary. The suicidal management plan that will be followed has substantial empirical support for its efficacy (Chiles & Strosahl, 2005) and is the plan that is recommended for use by the American Psychiatric Association.

In the proposed study we will use the FDA definition of adverse events (AE) and serious adverse events (SAE). Any SAE, whether or not related to study intervention, will be reported immediately to both the IRB and VA Centralized DMC and will be followed by an additional letter detailing the nature of the SAE. In the event that a participant either withdraws from the study or the site PI's (with consultation of the DMC) decide to discontinue a participant due to a SAE, the participant will be monitored by the site PI via ongoing status assessment until (a) a resolution is reached (e.g., the problem has resolved or stabilized with no further change expected), (b) the SAE is determined to be clearly unrelated to the study intervention, or (c) the SAE results in death. Outcomes of SAEs will be regularly reported to VA Centralized DMC (and the VA Boston and VA Providence IRB). A summary of the SAEs that occurred during the previous year will be included in the annual progress report as well as in the annual IRB renewal. Suicidal ideation and AEs will be formally assessed immediately after treatment and referrals for further care will be made as needed.

Under the arrangement to conduct the study on site at the VA Boston and VA Providence, the VA agrees to provide emergency services to anyone who participates in this project. We will have specifically outlined in the Informed Consent Form the availability of emergency services to veterans who may seek them during and after normal working hours. In the Informed Consent Form, we will provide specific information about emergency contacts. Participants are instructed to contact either [name] (VA Boston) or [name] (VA Providence) or their study therapist during business hours. If they have problems after hours, they are instructed to page the psychiatry on call service; the psychiatrist on call will then respond immediately to their call. This is the policy of the VA Boston and VA Providence for conduct of clinical trials at their sites. Veterans will also be provided with the phone number for the VA National Suicide Hotline.

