### **Outcome variables:**

**Measures of PTSD symptoms** will include the Clinician Administered PTSD Scale - 5 (CAPS -5) and the Posttraumatic Check List - 5 (PCL-S-5). The CAPS-5 has been discussed in Section D1 (Study Participants). The CAPS-5 will serve as the primary outcome measure for PTSD. Both measures derived from the CAPS-5 will be used (presence/absence of PTSD diagnosis and overall PTSD severity score

Other measures include:

- The PTSD Checklist-5 (PCL-5; Weathers, Litz, Huska, & Keane, 1994) is self-report measure of PTSD, that corresponds to the DSM-5 symptoms of PTSD. Like the CAPS, the PCL can be scored to yield an overall severity score (total score). Psychometric properties of the prior PCL are sound (Weathers et al., 1994). The proposed project will use the PCL-S-5, a version that requests individuals to state the index event for which they are rating symptoms. In addition to the assessment map provided in Table 4, the PCL5 will be administered weekly during treatment, in order to track participant risk. Greater details about how the PCL data will be used to assure participant safety can be found in Section E.2.

**Measures of distress and impairment** Three subscales of the Medical Outcomes Study Short-Form Health Survey (SF-36; Ware & Sherbourne, 1992) will be used to index objective role functioning/impairment. These scales are the Role Limitations due to Physical Problems (role-physical), Role Limitations due to Emotional Problems (role-emotional), and Social Functioning subscales which appear to be minimally confounded with psychopathology. All three of these subscales have shown factorial validity and discriminative validity (Ware & Sherbourne, 1992).

- **Health care utilization** will be examined as an exploratory aim to investigate the effect of PTSD group treatment on health care utilization. This measure will be evaluated via record tracking. Veterans may obtain medical care within or outside of the VA system. When men initially enroll in the project, we will ask the names of their medical providers. Physician records in the VA system can be electronically accessed using the CPRS system. For physicians outside of the VA system, we will seek a signed release of information, which will permit contact to track the number of visits. The Project Coordinator will keep monthly records of the number of medical visits (excluding wellness visits) for each participant.

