The study analyses will include all cases that were randomized into the trial, including individuals who dropped out of treatment. Thus, the distinction between ITT and completer analyses becomes artificial. Greater detail about the proposed analytic approach is discussed in the next section. We intend to contact participants who voluntarily drop out of treatment during what would have been their mid, post- and follow-up assessments, in order to provide as complete a data set (and effect size estimates) as possible.

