### **Potential Risks**

Treatment: Some risks are associated with the administration of any psychosocial treatment. In this study, the primary risk for both GCBT and SGP is the evocation of uncomfortable levels of anxiety or other emotions during the treatment sessions. Some patients may find sessions or assignments stressful and react to them with anxiety or anger. The GCBT carries an additional risk that exposure-based homework assignments may carry a likelihood of temporarily increasing PTSD symptoms. Recognizing this, the therapists assigned to this condition will alert participants to expect a possible increase in symptoms, to facilitate management of this should it occur. In addition, there will be a period of time between when participants are initially assessed and when there are a sufficient number of participants to randomize to a group treatment. We do not anticipate any adverse effects while participants are waiting for the group to begin. However, these individuals will be regularly monitored by the project coordinator and by Drs. [name] and [name] at their respective sites.

Recording: Some participants may feel uncomfortable about the assessment and treatment sessions being recorded (necessary for supervision and treatment adherence checks). However, this will be a required procedure. The purpose of the recording will be explained, confidentiality will be respected, and both informed consent and authorization for recording will be obtained as per requirements put forth by the Healthcare Information Portability and Accountability Act (HIPAA). Digital recordings will be marked only by subject identification codes, stored on a secured server that is pass-word protected, and only available to study personnel. Adherence rating sheets will also be stored in a locked cabinet located within the project coordinator's office.

Diagnostic Interviews, Self-Report Measures and Assessor Ratings: Some discomfort associated with the recording may occur as well as some potential distress when discussing traumatic experiences during the assessment interviews. These situations will be handled as described above.

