3. Displaying repeated disruptive behavior within the group treatment setting (examples include being sarcastic towards therapists or other group members, routinely arriving late by 30 minutes or more, hi-jacking the scheduled group content in order to direct attention to his own agenda). If there is a question about an individual's behavior during group, [name] will review the treatment recording and determine, in consultation with the other investigators on this application, if the veteran should be dropped from the trial.

Participants will be instructed to contact study personnel at any time (including during the follow-up interval) in the event of worsening of symptoms or relapse. Participants whose clinical condition has deteriorated will be removed from the study and given appropriate clinical care.

Participants failing to benefit from the study treatments will be provided with, or referred to, appropriate clinical care. Participants who begin treatment and experience adverse outcomes sufficient to require removal from the study will receive appropriate clinical care.

As in any type of treatment or clinical research program, participants' confidentiality must be carefully guarded and respected. All data with identifying information will be stored in locked files or password-protected computer files. Data being analyzed will be identified by subject codes, and identifying information will be removed. The identity of participants will not be revealed in the presentation or publication of any results from the project. All project staff will be educated about the importance of strictly respecting participants' rights to confidentiality and will have completed relevant training courses including proper practice in accordance with HIPAA regulations, protection of human subjects, and computer security.

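### The only stated formal assessment of non-serious adverse events comes after treatment, and men removed early have none stated

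*Combined protocol and SAP*

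**What the plan says.** Section E.5 adopts the FDA definitions of AE and SAE. SAEs go at once to the IRB and the DMC. For other events it gives one formal time: "Suicidal ideation and AEs will be formally assessed immediately after treatment and referrals for further care will be made as needed". No recall window is stated. The yearly summary is limited to serious events: "A summary of the SAEs that occurred during the previous year will be included in the annual progress report".

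Several safeguards operate during treatment:

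- Section D.4 (Outcome variables) says "the PCL5 will be administered weekly during treatment, in order to track participant risk", and adds: "Greater details about how the PCL data will be used to assure participant safety can be found in Section E.2".
- Section E.2 (Protection against risk) promises monitoring by project staff in every phase. It lists three explicit reasons for exclusion during the trial: psychotic symptoms, active suicidality or homicidality with intent, and repeated disruption. It also says: "Participants whose clinical condition has deteriorated will be removed from the study and given appropriate clinical care".
- Section E.5 sets out suicide-risk escalation. It also has the DMC review decisions about individual men "when investigators move into risk management protocols because of adverse events or clinical deterioration".

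Section E.1 (Potential Risks) says of GCBT that "exposure-based homework assignments may carry a likelihood of temporarily increasing PTSD symptoms", and has its therapists warn men of this.

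On leavers, the Analytic approach text says: "We intend to contact participants who voluntarily drop out of treatment". This is to happen at what would have been their mid-treatment, post-treatment and follow-up assessments. Section E.5 has the site PI follow men who leave because of an SAE.

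**The concern.** A safety question put once, after a 14-session course, is a weak way to learn about events that came and went during it. The risk that the plan attributes to GCBT alone is of exactly that kind: a temporary rise in symptoms while exposure homework is under way.

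The men whose experience matters most for harm may be those who do not finish. The plan provides later contact for voluntary drop-outs and follow-up for SAE exits. A man removed for deterioration or disruption without an SAE fits neither provision. What is at stake is the completeness of the tolerability record in both arms, and hence what the DMC and the final report can say about non-serious harm.

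**Working it through.** The plan states no figure to reproduce here. The check is mainly a comparison of text.

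**1. Where AEs are asked about.**

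- Before treatment and during follow-up, the coordinator makes contact every 3 to 4 weeks (E.2). This is not described as AE collection.
- During the 14 sessions there is a weekly PCL-5 (D.4), weekly therapist supervision (D.3) and consultation if suicide risk rises (E.5). None is described as asking about or recording AEs. Stated formal AE assessments: 0.
- Immediately after treatment there is 1 (E.5). I read this as after the course, since the text does not say after each session.

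**2. Who is covered on leaving.** Voluntary drop-outs are covered by later contact (Analytic approach), and SAE exits by site PI follow-up (E.5). Men removed under E.2 without an SAE get clinical care, with no AE assessment stated.

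**3. What is compared by arm.** D.7.d plans reliable change on CAPS total in each arm at post-treatment and 6 months. A rise that has settled by post-treatment would not show. D.7.a (Hypothesis 1) plans a growth model for the PCL with treatment condition as predictor. That estimates average change, not how many men worsened. No AE summary by arm is stated.

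**4. The promised PCL-5 detail.** E.2 does not mention the PCL, and neither does E.5. The purpose is stated in D.4; the trigger, reviewer and action are not.

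**5. Burden of asking at each session.** 14 sessions x 196 men = 2,744 entries at most; x 2 for double entry = 5,488 keyings.

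**6. Precision of a by-arm AE table.** Assume 20% of men have an AE. With 98 per arm, half-width = 1.96 x sqrt(2 x 0.2 x 0.8 / 98 x DE).

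- No clustering, DE = 1: 11.2 points.
- Plan's rho of 0.11 and groups of 7, DE = 1 + 6 x 0.11 = 1.66: 14.4 points.

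The table is therefore descriptive.

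**7. Why a PCL-5 count from pre-treatment needs care.** Take an illustrative rule: flag a man if any of 14 weekly scores exceeds his pre-treatment score by the 95% reliable-change threshold. Simulation used d_t = (e_t - e_0)/sqrt(2) + f x u_t + mean shift, flagged if above 1.96. Here f = 0 is measurement error only, and f = 0.5 adds an assumed true weekly fluctuation.

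| Scenario | f = 0 | f = 0.5 |
|---|---|---|
| No change, no rise | 17.4% | 28.1% |
| Improves by one threshold by week 14, no rise | 4.3% | 8.4% |
| Same improvement, true one-threshold rise in weeks 6-8 | 34% | 41% |

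Suppose SGP men neither improve nor rise, while GCBT men improve and 30% have the rise (assumptions). Flagged in GCBT:

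- f = 0: 0.7 x 4.3 + 0.3 x 34 = 13.2%, against 17.4% in SGP.
- f = 0.5: 0.7 x 8.4 + 0.3 x 41 = 18.2%, against 28.1% in SGP.

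The arm with real worsening looks safer. At f = 0 the reversal lasts until the share with a rise reaches (17.4 - 4.3)/(34 - 4.3) = 44%. If both arms improved equally it would vanish (13.2% against 4.3%). The bias follows the difference in improvement, which the trial hypothesises to favour GCBT.

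**The case against.** The best case for the plan is that monitoring during treatment is already substantial and that absence cannot be fully shown. The Table 4 assessment map, the appendices and some text ahead of Section C.2 are not available. Section D.6 also promises an operations manual covering assessment steps, case management and data management, where AE forms or cut-offs could sit. This stands as a caveat: an AE entry elsewhere cannot be excluded. It does not supply the PCL-5 detail, because D.4 points to E.2 and E.2 is visible.

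Three stronger readings are tempting, and the documents do not support them.

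- That the trial has no safety monitoring during treatment, or no safety use for the weekly PCL-5. D.4 states the use, and E.2 and E.5 describe monitoring, escalation and DMC review.
- That no by-arm analysis could show worsening. CAPS reliable change by arm is planned, and nothing limits it to improvement. The accurate statement is narrower: nothing planned counts temporary worsening during treatment.
- That harmed men will be lost from the data. DMC review means individual deteriorations are identified; what is missing is a stated AE assessment for men removed.

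It is also fair to say that asking at every session is partly a preference, and that the simulation describes an illustrative rule, not the size of the gap. Both stand. The amount of under-recording cannot be estimated from the documents.

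**Conclusion.** The concern holds in limited form. On the visible text, non-serious AEs during the 14 sessions depend on recall or spontaneous report, and men removed for deterioration or disruption have no stated AE assessment. The added GCBT risk named in E.1 would not be counted by any planned by-arm analysis while it is occurring. The missing PCL-5 step in E.2 is a smaller, editorial gap.

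Severity is minor to moderate. Serious events and suicide risk are handled, and a reader should not infer any effect on the efficacy comparison: randomisation, sample size and the primary model are untouched. The conclusion assumes that the E.5 sentence means after the whole course and that Table 4 holds no AE row. If it does hold one, the collection part falls away and E.5 need only be aligned with it. This is a cheap improvement, not a flaw in the main result.

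**What to change.** 1. At existing sessions in both arms, alongside the weekly PCL-5, ask one brief written AE question covering the time since the last session. Staff other than the blinded assessors should collect it.
2. Give the post-treatment AE form to every man who stops or is removed, whatever the reason.
3. Report AEs, SAEs and removals with reasons, descriptively by arm and for all randomised men, to the DMC and in the final report.
4. As a minor completion, write into E.2 the PCL-5 review step that D.4 promises: what prompts a review, who does it and what may follow.
5. If PCL-5 worsening is tabulated by arm, show rises from the previous week as well as from pre-treatment. State that the count from pre-treatment is biased towards the arm that improves more and is not evidence of relative safety.

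The cost is at most 2,744 short entries (5,488 keyings), a short addition to E.2 and one table. GCBT men are warned to expect a rise and may report more AEs for that reason, so the by-arm AE counts need a note saying so.

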## **Resources**

### **VA Boston Healthcare System – Primary site**

The National Center for PTSD, Behavioral Science Division (BSD) at VA Boston Healthcare System is the primary site for the proposed project, and represents one of two recruitment sites for the study. The National Center for PTSD is mandated by public law 98-528 as a specialized center within the Department of Veterans Affairs devoted to research and training in all aspects of PTSD. The BSD is located in the Jamaica Plain campus of the VA Boston Healthcare System and is integrated with the PTSD outpatient clinic at the Jamaica Plain campus. The Jamaica Plain campus is conveniently located, with several public transportation alternatives (train and bus lines) that have stops either directly at the medical center or within a few blocks from the medical center. In addition, parking at the medical center is free to visitors. Shuttle service runs between the Jamaica Plain VA campus and the other VA Boston campuses, including the Brockton campus and the community based outpatient clinics. In addition, shuttle buses transport veterans from community based outpatient clinics in the surrounding area (e.g., Worcester) to the Jamaica Plain campus. Thus, the Jamaica Plain campus is easily accessible to veterans residing in the greater Boston area.

The BSD staff is comprised of 14 doctoral-level clinical psychologists with a broad range of expertise in the area of posttraumatic stress who work closely together within a collaborative center. In addition to the BSD staff, the PTSD Clinic has 6 Staff Psychologists. BSD also houses 8 or more post-doctoral fellows, 2 pre-doctoral interns, 2 full-time LAN administrator/programmers, 1 administrative officer, 1 full-time clerk for scheduling appointments, and approximately 15 full-time research assistants.

The BSD occupies two vertically adjacent floors in one wing of the main building on the Jamaica Plain Campus of VA Boston Healthcare System. BSD space comprises over 3200 square feet and includes over 30 offices, 4 conference rooms, 5 laboratory rooms, 2 computer rooms, multiple testing/therapy rooms, storage areas, and two staff kitchens. The division also controls 1700 linear feet of securely enclosed, track-mounted storage, located in the basement of the building, which is used for long-term retention of raw research data.

Staff working on this study will be housed in office space within BSD.

Other Resources:

[name], Associate Chief of Staff for Research, at the VA Boston Healthcare System and Director of BSD, is a Principal Investigator on a T32 training grant funded by NIMH that provides for post-doctoral clinical research training in PTSD to four fellows on a bi-annual basis. [name] (Primary PI on this proposal) serves as Director of this fellowship program. The four post-doctoral fellows are very engaged in all aspects of ongoing research projects in BSD, and often assist with the conduct of assessments for study protocols.

Windows-compatible software of various types is available to all BSD staff via the network. Specific examples of the software include MS Word and WordPerfect for word processing, Excel for spreadsheets, Access and SQL Server for databases, PowerPoint for graphics applications, Adobe Illustrator and Photoshop for digital image manipulation, Adobe Acrobat for PDF file manipulation, and SPSS, S-Plus, LISREL, M-Plus, EQS, AMOS, HLM, and Solas for statistical analysis. Teleform software is used to create customized scannable forms for data collection and automated data entry, and Alchemy software is used for electronic archiving of research forms.

The BSD subscribes to the PsycInfo service for literature searches, and to the PsycArticles service for full text electronic access to journals published by the American Psychological Association. Both of these can be accessed directly from the LAN and remotely. In addition, through the BSD's affiliation with Boston University School of Medicine, there is electronic and physical access to journal articles, books, and databases. Commercial software is available for functions such as creating and searching customized bibliographic databases, statistical power calculations, and modem and fax communication.

